### **6.2 Objectives**

1. Identify all patients with a condition that would qualify them for emergency abdominal surgery, both laparotomy and keyhole (laparoscopic) procedures, regardless of whether they had surgery

or not. This will be done by filtering electronic hospital records for appropriate diagnosis and operation codes.

2. Provide updated estimates of the average risk of death for different treatment options, including surgical and non-surgical intervention, using statistical analysis of short-term and long-term outcomes. Describe health characteristics of the typical patient population receiving one of the treatment options, based on their clinical data and an established risk index.
3. Logistic regression will be used to predict the risk of death for each patient group and each treatment option, which will allow identification of the best care pathways given a patient's health characteristics.
4. Identify patients who would have likely benefited from a different care pathway than the one they received, using machine learning classification algorithms

Our analysis will form the foundation for the establishment of four well-defined care pathway options, each with the patient's best interest in mind: laparotomy, laparoscopy, other alternative treatment, and end of life care.

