### 7.2 Primary and Secondary Endpoints/Outcome Measures

The primary outcomes to be assessed will be length-of-stay, in-hospital, short-term (30-day), and long-term (1- year) mortality.

Secondary outcomes include: long-term complications, such as re-admission to hospital, additional abdominal surgery and the development of new medical conditions as well as the relationships between any of these outcomes and patient characteristics.

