#### **7.4 Study cohort**

Data will be derived from electronic patient records collected as part of routine clinical patient care on all general adult wards (excluding maternity) between 2013 (beginning of NELA and collection of data of interest) and 2020.

All patients with a condition that would qualify them for emergency abdominal surgery will be identified, using their ICD-10 diagnosis and OPSC-4 procedure codes which are part of the electronic patient record. Once patients have been identified, they will be screened against the inclusion/exclusion criteria (see below). For each patient, this will include only the first intervention within the study period in the analysis. Subsequent admissions with an abdominal condition or subsequent interventions will be classified as complication and therefore considered as an outcome.

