##### Exclusion criteria:

- Maternity admissions during/after pregnancy
- Patients admitted or undergoing abdominal surgery for a second time or more

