### 10.2 Data analysis

Extracted data will be cleaned and quality controlled prior to analysis to ensure all relevant patients have been extracted. Given that our analysis will use only routinely collected, clinical data, missing values are unlikely to pose an issue. Initial analysis of 2018 data confirmed that clinical data within 24h of admission was almost fully complete for a remarkable >97% of admissions, meaning there is likely no need to impute data. We will test whether excluding admissions with missing data will introduce bias.

Our analysis can be broken down into the following steps:

- Comparison of the four treatment groups based on demographics, outcomes and medical pathway. This will include calculating mortality and long-term complication rates (Objective 2).
- Construct and compare risk models for each treatment group to predict short-term and long-term risk and to investigate the effect of both patient and hospital-level factors on outcome (Objective 3).

- Identify patients in each group who are abnormal for the group and might have fared better with a different treatment, using clustering algorithms (Objective 4).

After splitting the data set into subsets for each of the four patient groups using diagnosis and procedure codes (see above), mortality and long-term complication rates will be calculated for each group. Longer-term follow-up will include rates of re-admission to hospital, additional theatre visits and development of new medical conditions, within one year of initial admission with an abdominal emergency. Results will provide updated estimates of the average risks of different surgical procedures as well as the risk of not having surgery. Results will be compared with P-POSSUM mortality. Patient groups will further be characterised the using patient factors. Parameters of interest will include but are not limited to age, sex, mortality, long-term complication rates, admission early warning scores (NEWS, LDTEWS and LDTEWS:NEWS), frailty, medical history (previous ICD-10 codes).

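### Section 7.4 takes the first intervention as the index event and excludes repeat patients, while the same section and section 10.2 follow patients from initial admission and count repeat events as outcomes

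*Protocol*

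**What the plan says.** Five statements in the protocol bear on who is in the cohort, in which group, and from when.

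- **Index event (section 7.4, Study cohort):** "For each patient, this will include only the first intervention within the study period in the analysis".
- **Later events (section 7.4, next sentence):** "Subsequent admissions with an abdominal condition or subsequent interventions will be classified as complication and therefore considered as an outcome".
- **Exclusion (section 7.4, Exclusion criteria; identical in the synopsis, section 2):** "Patients admitted or undergoing abdominal surgery for a second time or more". It has no time window and does not say whether the person or only the later episode is dropped.
- **Outcomes (section 7.2):** secondary outcomes are "long-term complications, such as re-admission to hospital, additional abdominal surgery and the development of new medical conditions". Sections 9.1, 10.1 and 10.2 also plan for re-admission and further surgery.
- **Clock and grouping (section 10.2):** longer-term follow-up is counted "within one year of initial admission with an abdominal emergency". Groups are formed thus: "After splitting the data set into subsets for each of the four patient groups using diagnosis and procedure codes". No time point for the assignment is given.

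Objective 1 (section 6.2) requires patients to be included "regardless of whether they had surgery", so the cohort is meant to contain people who never have a procedure.

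**The concern.** The protocol fixes the index event, the exclusion and the follow-up clock in separate sentences that do not fit together. The patient who exposes this is one admitted with an abdominal emergency, managed without surgery, discharged, and operated on at a later admission. Two analysts following the text could place that patient differently.

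The non-operative group is the reason for the study, and section 10.2 promises an estimate of the risk of not having surgery. Patients who survive non-operative care and later need an operation belong in that group's denominator, and the operation is one of its outcomes. They also matter for Objective 4, which looks for patients who might have done better on another pathway. Moving or removing them alters a primary outcome (mortality by treatment group) and the secondary outcomes of re-admission and additional surgery.

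**Working it through.** **Step 1. The same patient under each rule as worded**

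| Rule | Where | Result for this patient |
|---|---|---|
| A. First admission is the index; later events are outcomes | 7.4, second sentence quoted; 10.2 clock | Non-operative, with a re-admission and an operation as outcomes |
| B. First intervention, read as first procedure, is the index | 7.4, index sentence | Surgical; the survived non-operative episode drops out |
| C. Anyone admitted or operated on a second time is excluded | 7.4 exclusion; synopsis | Not in the cohort |

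Reading the exclusion as applying to episodes does not fully remove the conflict. If an intervention is a procedure, this patient's first intervention falls in a second admission: the index sentence selects it and the exclusion screens it out. Rule B also gives no index event to a patient who never has a procedure.

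**Step 2. The plan's own figures (section 8)**

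Inputs: 901 patients in 2018, 530 with surgery, 23 and 28 in-hospital deaths with and without surgery, and 6.5 years.

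- Non-operative: 901 − 530 = 371, or 371/901 = 41%.
- Scaled cohort: 901 × 6.5 = 5,856.5 (stated: over 5,800). Surgical: 530 × 6.5 = 3,445 (stated: over 3,400).
- Mortality: 23/530 = 4.34% (stated 4.3%); 28/371 = 7.55% (stated 7.6%, a difference of rounding size).
- Non-operative over 6.5 years: 371 × 6.5 = 2,411.5 patients, with 28 × 6.5 = 182 in-hospital deaths.

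**Step 3. Illustration of rules B and C**

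Let c be the share of the non-operative group operated on at a later admission. The protocol gives no value, so c = 2% to 20% is an assumption. The 2018 split is taken as if it followed rule A. These patients survived their first admission by definition, so moving or removing them leaves the 182 deaths in place and shrinks the denominator:

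non-operative in-hospital mortality = 182 / [2,411.5 × (1 − c)]

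| c | Patients moved or removed | Rule A | Rule B or C | Cohort under C (crossovers only removed) |
|---|---|---|---|---|
| 2% | 48 | 7.55% | 7.70% | 5,808 |
| 5% | 121 | 7.55% | 7.94% | 5,736 |
| 10% | 241 | 7.55% | 8.39% | 5,615 |
| 20% | 482 | 7.55% | 9.43% | 5,374 |

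The last column understates rule C, because a person-level exclusion would also remove surgical patients with a second admission or operation. The effect on surgical mortality under rule B depends on how crossovers fare after their operation, which the protocol does not give. The shift in 30-day and 1-year mortality is not computed for the same reason.

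**Step 4. Effect on the secondary outcomes**

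Under rule B, the later operation becomes the index treatment of a surgical patient and is lost as an outcome of non-operative care. Under rule C applied to persons, every patient with a second abdominal operation leaves the cohort, so that outcome cannot occur in the data.

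**The case against.** The strongest defence is that the protocol already means rule A. Sections 7.2, 9.1, 10.1 and 10.2 all plan to measure re-admission and further surgery, so the exclusion is naturally read as barring repeat episodes from entering as new cases. Objective 2 (section 6.2) speaks of surgical and non-surgical intervention, so the first intervention could mean the first treatment episode. Eligibility is tied to the day of admission, and section 10.2 sets the one-year clock at the initial admission. Finer episode rules can be left to a statistical analysis plan.

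Much of this stands: rule A fits the document best. The wording still contradicts it. The exclusion is written for patients, whereas the maternity exclusion beside it is written for admissions, and section 7.4 says that identified patients are screened against these criteria. Section 7.4 names admissions and interventions separately, and section 15.3 allows for patients with no intervention. Two stated rules give a wrong result if followed as written, which is more than detail left for later.

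Three stronger inferences are tempting and should not be drawn:

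- *That the plan sets re-admission and re-operation rates to zero.* This needs a literal person-level exclusion, which conflicts with the four sections that plan these outcomes.
- *That crossovers' follow-up starts at a later, sicker admission.* Section 10.2 sets the one-year clock at initial admission, and nothing in the document describes how sick patients are at a later admission.
- *That a known number of patients changes group.* No crossover rate is given. The 371 also include 28 in-hospital deaths, who cannot cross over, and may include interventional radiology patients, who already had an intervention at the first admission.

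**Conclusion.** The inconsistency is real and should be reconciled before the cohort is built. Section 7.4's index sentence and the exclusion (also in the synopsis) conflict with section 7.4's own treatment of later events, with the outcomes in section 7.2, and with the follow-up clock in section 10.2. It is a conflict of wording with a coherent intended reading behind it; it does not show that the planned results will be biased.

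The harm depends on which rule is implemented. Under rule A there is none. If the index were the first procedure, non-operative in-hospital mortality would be overstated: 7.55% becomes about 7.7% to 9.4% for an assumed crossover of 2% to 20%, and later surgery would be lost as an outcome of that group. If the exclusion were applied to persons, additional abdominal surgery could not be observed. The percentages are illustrative and rest on the assumed crossover share and on the 2018 counts scaled to 6.5 years. The contradiction itself rests on neither.

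**What to change.** Reword the synopsis (section 2) and section 7.4, including its exclusion criteria, as follows:

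1. Index every patient on the first qualifying admission in the study period, whether or not a procedure took place. This replaces the first-intervention sentence.
2. Assign the treatment group from that admission only, and state how a change of treatment within that admission is classified.
3. Start all outcome clocks at that admission, consistent with section 10.2.
4. Count any later abdominal admission or operation within one year as an outcome in the original group.
5. Reword the exclusion so that second and later admissions or operations are not entered as new index episodes, while the patient stays in the cohort.

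The cost is a wording change. No new data are needed, since section 9.1 already plans linked data on re-admission and subsequent abdominal surgery.

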Study Participants	
Data will be derived from electronic patient records collected as part of routine clinical patient care on all general adult wards (excluding maternity) between 2013 and 2020.
 
Inclusion criteria:
 
 
• Must have an acute intestinal condition, based on their ICD-10 codes and OPSC-4 codes
 
• Must be <math>\geq 16</math> years of age at the time of admission
 
• Have at least one full set of vital signs recorded on the day of admission
 
• Have at least one full set of routine blood tests recorded on the day of admission
 
 
Exclusion criteria:
 
 
• Maternity admissions during/after pregnancy
 
• Patients admitted or undergoing abdominal surgery for a second time or more
 
 
Using OPCS-4 codes from PAS and TheatreMan™ and NELA data, we will then identify patients who had an emergency laparotomy, and those who had a laparoscopic procedure. We aim to identify a further group where treatment is futile, suggesting that an early focus on end of life care might be appropriate.

Planned Sample Size	2,500
Follow-up duration	1 year (retrospectively)

Planned Study Period	01 Dec 2020 – 31 May 2021
Primary Objective	Provide mortality rates for different treatment options, and analysis of short- and long-term outcomes.
Secondary Objectives	Define patient sub-groups with similar health characteristics based on clinical data and an established risk index.  Use statistical analysis to predict the risk of death for each patient group and treatment option, which will allow us to identify the best care pathways for each cluster.
Primary Endpoint	Mortality risk for each treatment group
Secondary Endpoints	Risk of other outcomes and long-term complications and association between patient factors and these outcomes
Intervention (s)	N/A

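### Surgical groups are assigned from procedure codes with no time limit from admission, so deaths while awaiting surgery count as non-surgical and the surgery versus no-surgery mortality contrast is biased towards surgery

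*Protocol*

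**What the plan says.** The Synopsis (Study Participants) identifies the surgical patients from records of procedures performed: "Using OPCS-4 codes from PAS and TheatreMan™ and NELA data, we will then identify patients who had an emergency laparotomy", with laparoscopic cases found in the same way. Section 7.4 fixes which procedure counts: "this will include only the first intervention within the study period". Later interventions are treated as complications. Section 10.2 computes mortality "After splitting the data set into subsets for each of the four patient groups using diagnosis and procedure codes". None of these places says how soon after admission a procedure must occur to define the group, or how to classify a patient who dies before a planned operation.

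The primary outcomes in section 7.2 are "length-of-stay, in-hospital, short-term (30-day), and long-term (1- year) mortality". The only follow-up origin given is in section 10.2, where readmission, further theatre visits and new conditions are counted "within one year of initial admission with an abdominal emergency". The origin for 30-day and 1-year mortality is not stated.

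The contrast between groups is intended. Section 10.2 says "Results will provide updated estimates of the average risks of different surgical procedures as well as the risk of not having surgery", and it plans chi-squared tests of proportions between groups with pairwise comparisons at the 5% level. Sections 6.2 (objective 3) and 7.1 use the modelled risks to choose best care pathways and lower-risk options.

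**The concern.** A procedure code exists only if the patient survived to the procedure. Grouping by such codes and then comparing mortality from a common start gives the surgical groups a stretch of time in which, by construction, nobody can die. Deaths in that stretch go to the non-surgical side, including deaths of patients already accepted for theatre. This is immortal time bias, and its direction follows from the rule.

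Section 4.3 describes these conditions as time-critical, so some deaths soon after admission are plausible. The results are meant to inform advice on laparotomy against alternatives (section 4.2). Part of any excess mortality without surgery could therefore come from the grouping rule and be read as a benefit of operating. Modelling each group separately on admission characteristics does not correct this, because the error lies in who is placed in which group.

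**Working it through.** **Inputs (Protocol, section 8, 2018 data).** 901 patients; 530 had surgery; 23 in-hospital deaths with surgery and 28 without.

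**Reproducing the stated figures.**
- No surgery: 901 − 530 = 371.
- Surgery: 23/530 = 4.34% (stated 4.3%).
- No surgery: 28/371 = 7.55% (stated 7.6%). With 41% of 901 as denominator, 28/369.4 = 7.58%, so the small difference is rounding.
- Scaling: 901 × 6.5 = 5,856.5 (stated as over 5,800) and 530 × 6.5 = 3,445 (stated as over 3,400).
- Crude gap: 7.55 − 4.34 = 3.21 percentage points; uncorrected chi-squared p = 0.040.

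**Sensitivity.** Let k be the number of the 28 deaths that occurred while the patient was awaiting surgery. The protocol gives neither time to surgery nor timing of deaths, so k is an assumption throughout.

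(a) Exclude these deaths from the no-surgery group, risk = (28 − k)/(371 − k), holding surgery at 23/530 = 4.34%:
- k = 1: 27/370 = 7.30%, p = 0.057
- k = 4: 24/367 = 6.54%, p = 0.15
- k = 7: 21/364 = 5.77%, p = 0.33

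(b) Move them to the surgical strategy, surgery risk = (23 + k)/(530 + k), with the no-surgery risk as in (a):
- k = 1: 24/531 = 4.52% v 7.30%, p = 0.076
- k = 4: 27/534 = 5.06% v 6.54%, p = 0.34
- k = 7: 30/537 = 5.59% v 5.77%, p = 0.91

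Scaling (b) to 6.5 years, the gap remains significant at the equivalent of k = 4 per year (p = 0.016) but not at k = 5 (p = 0.09).

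Neither calculation is a landmark analysis. A true landmark would also remove surgical patients who died before it and would count those operated on later as not yet operated. The 2018 counts do not allow this to be computed.

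**Check of direction with no treatment effect.** A simulation gave every patient the same 30-day risk, 51/901 = 5.66% (the 2018 in-hospital figure, borrowed). It assumed 59% intended for surgery independently of risk, and a mean wait of 0.5 to 4 days. Grouping by whether surgery happened produced a spurious gap favouring surgery of 0.2 to 1.8 points under a constant hazard, and 1.5 to 4.2 points when deaths were concentrated early (Weibull shape 0.5). This confirms the direction. The sizes depend on the assumed inputs and are not estimates for this cohort.

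**The case against.** **The time window is unstated, and an analysis plan could supply one.** It is tempting to read the protocol as coding treatment over the whole admission, but it does not say so. The sentence in section 7.4 selects among several interventions. However, the rule as written admits a procedure at any time, and an analysis that follows it will charge pre-operative deaths to no surgery. The point therefore rests on the stated rule and not only on missing detail.

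**The primary objective is descriptive.** The Synopsis asks for mortality rates by treatment option, and a patient who died unoperated is correctly described as unoperated. This stands. A reader might infer that the primary rates are invalid, but only the comparative use is affected.

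**The mortality clock.** A reader might infer that 30-day mortality runs from operation in surgical patients and from admission in the rest, which would enlarge the bias. Nothing in the protocol says this. The origin is unstated, and the one origin given for other events is admission.

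**Size.** Under calculation (a), removing 12 of the 28 deaths (43%) would give 16/359 = 4.5% and close the gap, so a reader might infer that the bias explains the whole difference. The protocol does not support that. Among the reasons for no surgery quoted in section 4.3 from the earlier cohort of patients declined laparotomy, 74% were judged unfit, and death while waiting is not listed. Patients judged unfit who die early are not misclassified. Borrowing the entire 16% undocumented share as an assumed upper value gives 0.16 × 28 = 4.5 deaths. In addition, the requirement for full vital signs and blood tests on the day of admission (section 7.4, inclusion criteria) already removes some of the earliest deaths.

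**Confounding by fitness** is separate and probably larger. It does not offset this bias, since both make surgery look better.

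**Conclusion.** The concern holds for the surgery versus no-surgery mortality contrast, and for any contrast with a procedure that tends to come late, such as interventional radiology. It applies where that contrast is tested and used to identify lower-risk options. The direction, in favour of surgery, follows from the grouping rule. Laparotomy versus laparoscopy is little affected, because both groups must survive to theatre.

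The size cannot be established from the protocol. Under an assumed 1 to 7 pre-operative deaths among the 28 in 2018, excluding them lowers the no-surgery risk from 7.5% to between 7.3% and 5.8%, against 4.3% with surgery. This shows that the contrast is sensitive to a few deaths; it does not show how much of the gap is artefact. Nor does the protocol support saying that the bias favours the study's hypothesis: the Synopsis states only the aim of improving care with or without surgery. The point should be dealt with before the comparative analysis, but it does not undermine the study.

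**What to change.** - State admission as time zero for 30-day and 1-year mortality in all four groups.
- Keep the descriptive rates by treatment received as planned.
- For the surgery versus no-surgery comparison, add a landmark analysis. Classify patients by treatment received by a fixed time from admission (for example 24 h, with 48 h and 72 h as sensitivity analyses) and count only later deaths in all groups.
- Report deaths before each landmark separately, for operated and unoperated patients.

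The cost is a few sentences in the protocol or SAP and a derived time-to-procedure variable. The admission, theatre and linked mortality records in section 9.1 should hold what is needed, provided that procedure and death dates, with times where available, are extracted as well as yes/no indicators. No additional patients are required.

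The downside is that early deaths, including early post-operative deaths, leave the comparison, and that patients operated on after the landmark count as not yet operated. This is why several landmarks should be shown and the pre-landmark deaths reported beside them. The landmark analysis does not address confounding by fitness for surgery.
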